3.3 General Handling of Missing Data

For incomplete dates related to concomitant medications, the dates will be imputed as follows:

If the incomplete date is a start/onset date:

(1) if the month and year are present, then the first day of the month will be used for day.

(2) if only the year is present, then the first day of January will be used for month and day.

If the incomplete date is an end date:

(1) if the month and year are present, then the last day of the month will be used for day.(2) if only the year is present, then the last day of December will be used for month and day. If the reported year is the same as the informed consent year, then the informed consent date will be used.

Dates that are completely missing will not be imputed.

Baseline values that are missing will not be imputed. Subjects who have missing subgroup values will not be included in that particular subgroup analyses.

If efficacy data are missing and the subject has not been deemed a success or failure the outcome will be categorized as unknown.

4. Subject Disposition

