16.1 Informed Consent

Every study subject (or the subject's legal representative) must provide written informed consent at Screening/Treatment Day 1, prior to participating in any Screening evaluations or any other study activities (see Section 21.3).

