6.1.1 Prior Medications

Prior medications are defined as medications taken and stopped prior to the first dose of study drug. The number and percentage of subjects who took prior medications will be presented by WHO therapeutic drug class and generic drug name.

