6.1.2 Concomitant Medications

Concomitant medications are defined as medications that are ongoing at or started after the first dose of study drug and started on or before the FU visit date, regardless of whether the stop date is missing. Medications with a stop date after the first dose of study drug are also considered concomitant medications. Medications with incomplete or missing dates will be handled as detailed in Section 3.3. A summary showing the number and percentage of subjects who took concomitant medications will be presented by WHO therapeutic drug class and generic drug name.

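### SAP 3.3 moves a medication end date known only as the consent year back to the consent date, giving some stops before starts and classing some on-treatment drugs as prior

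*SAP*

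**What the plan says.** SAP 3.3 opens its date rules with "For incomplete dates related to concomitant medications, the dates will be imputed as follows", then gives one block for start dates and one for end dates.

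- Start date, year only: "if only the year is present, then the first day of January will be used for month and day".
- End date, year only: "if only the year is present, then the last day of December will be used for month and day". The next sentence, still in the end-date block, reads "If the reported year is the same as the informed consent year, then the informed consent date will be used". The start-date block has no such sentence.
- Dates that are missing altogether are not imputed.

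The classification depends on these dates. SAP 6.1.1: "Prior medications are defined as medications taken and stopped prior to the first dose of study drug". SAP 6.1.2: "Concomitant medications are defined as medications that are ongoing at or started after the first dose of study drug", with start no later than the follow-up visit, and whether or not a stop date exists. It adds "Medications with a stop date after the first dose of study drug are also considered concomitant medications" and refers incomplete or missing dates to 3.3.

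On the timing of consent, Protocol 16.1 says each subject "must provide written informed consent at Screening/Treatment Day 1, prior to participating in any Screening evaluations or any other study activities". The visit window in SAP Table 1 runs from Day -1 to Day 1.

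**The concern.** For a stop date, an early imputed value shortens the period of use. Here the value is the consent date, which is the day before first dose or the same day. A rule that places every such stop at or before the start of treatment cannot describe a drug that was taken during treatment, and SAP 3.3 has no check that a stop falls on or after its start.

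What is at stake is the accuracy of the prior and concomitant medication summaries. Subjects may enter while on IV antifungal therapy, and medications are recorded from 28 days before Day 1, so drugs begun before first dose and continued after it are to be expected. Those are the drugs that can drop out of the concomitant table.

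**Working it through.** No figure in the plan needs reproducing, so the check is to apply the rules as printed.

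**Inputs.** Imputation rules from SAP 3.3; class definitions from SAP 6.1.1 and 6.1.2; consent on Day -1 or Day 1 from Protocol 16.1 and SAP Table 1. The calendar dates are assumed for illustration: first dose 11 March 2019 (Day 1), true stop 20 April 2019 (Day 41), stop recorded only as 2019.

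**Step 1: the imputed stop.** The reported year equals the consent year, so the stop becomes the consent date: 10 March (Day -1) or 11 March (Day 1).

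**Step 2: class and date order.**

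| Start as recorded | Start used | Consent Day -1: stop 10 March | Consent Day 1: stop 11 March |
|---|---|---|---|
| 1 March 2019 | 1 March | Prior | Stop equals first-dose date: ambiguous |
| March 2019 (true start Day 15) | 1 March | Prior | Ambiguous |
| 2019 (true start Day 15) | 1 January | Prior | Ambiguous |
| 25 March 2019 (Day 15) | 25 March | Concomitant; stop 15 days before start | Concomitant; stop 14 days before start |
| April 2019 | 1 April | Concomitant; stop 22 days before start | Concomitant; stop 21 days before start |

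Ambiguous means that the stop date is neither before nor after the first-dose date. The drug is concomitant only if it is read as ongoing at first dose.

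**Step 3: the same ten cases without the sentence.** With 31 December alone, all ten are concomitant and none ends before it starts. If the stop is also capped at last contact, taken here as Day 132 (Protocol 12.3 gives about 132 days; 11 March + 131 days = 20 July 2019), it falls after first dose and after every start in the table, so the result is the same.

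**Step 4: comparison within the SAP.**

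- The sentence reverses the direction of the rule immediately before it.
- SAP 8.1 sets an adverse event end date known only by year to 31 December, with no consent exception.
- A drug begun before first dose with no stop information is not imputed and stays concomitant under 6.1.2. Recording the year of the stop can make the same drug prior, so more information gives a worse answer.

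**Step 5: reach.** Assume consent dates spread evenly over a 365-day year. The share of on-study days after Day 1 that fall in the consent year, for follow-up of L days, is 1 - (L/2)/365.

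- L = 132: 1 - 66/365 = 82%
- L = 90: 1 - 45/365 = 88%
- L = 42: 1 - 21/365 = 94%

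So the exception, not the 31 December rule, would govern most year-only stops that occur on study. These are shares of days. They do not say how many records have a year-only stop.

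**The case against.** **Scope.** A reader might infer that every on-study drug with such a stop date becomes prior. SAP 6.1.2 does not support that: a known start after first dose makes the drug concomitant whatever its stop date. Prior status needs consent on Day -1 and a start known or imputed before first dose. This objection stands and sets the limits of the point.

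**Prohibited medication and the per-protocol population.** A reader might also infer that drugs vanish from the checks behind per-protocol exclusion. Nothing in the documents makes that link. SAP 4.2 relies on a separate deviation rules document and a review before database lock, and a by-subject medication listing is also produced. For the listed CYP3A4/5 inhibitors and inducers, Protocol 13.2 and Appendix A also bar use in the 48 hours or 14 days before enrollment. An imputed stop on Day -1 or Day 1 would fall inside those windows. This objection stands too.

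**Late imputation has its own error.** A drug truly stopped before the study, with only the year recorded, becomes concomitant under a 31 December rule. That is correct, but it is the direction the SAP's base rule already takes, and the one 6.1.2 takes for a wholly missing stop.

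**Rarity.** Start and stop times of drugs taken during therapy go on the eCRF, new drugs go in the diary, and visit data are due within 5 days. Year-only stops on study should be uncommon. This bears on size, not on whether the rule is right.

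**Layout.** The sentence may have been meant to cover start dates as well; the end-date fault then remains. It disappears only if the sentence was meant for start dates alone, which the printed text does not say.

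**Conclusion.** The point holds, and it is minor. As printed, a stop date known only as the consent year is imputed on or before the first-dose date. This yields impossible date orders for drugs started after first dose. For drugs that began, or are taken to have begun, before first dose and then continued, it yields a wrong class (consent on Day -1) or an undefined one (consent on Day 1).

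The documents do not give the number of records affected; it is probably small. The effect is on descriptive medication tables and listings in a single-arm study of about 30 subjects. The conclusion assumes only that the sentence belongs to the end-date block where it is printed, or to both blocks.

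**What to change.** Delete the consent-year sentence from the end-date rules in SAP 3.3. Impute a year-only end date as the earlier of 31 December of that year and the subject's last study contact, and state that an imputed stop may not precede the start.

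Moving the sentence to the start-date block is not a safe substitute: a year-only start set to the consent date could fall after a known stop before consent.

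The cost is a small change to the SAP text and the matching program step, with no new data. The remaining downside is that some drugs truly stopped before the study will be counted as concomitant. Flagging imputed dates in the by-subject listing would let a reader see which records these are.

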4.1 Disposition

Subject disposition in terms of the number and percentage of subjects enrolled by site will be tabulated. The number of subjects enrolled, number completing the study and reasons for discontinuation will be summarized.

The reason for study discontinuation may include any of the following: adverse event; death; disease relapse; progressive disease; lost to follow-up; physician decision; pregnancy; withdrawal by subject; other.

Subject disposition data will be presented in a listing.

4.2 Protocol Deviations

The investigator may not deviate from the protocol without a formal protocol amendment having been established and approved by an appropriate IRB, except when necessary to eliminate immediate hazards to the subject or when the change(s) involve(s) only logistical or administrative aspects of the study.

Major protocol deviations will be defined in the significant protocol deviations rules document. Each significant deviation will be assigned a rule number. As the study is ongoing, additional significant protocol deviations can also be spontaneously identified or defined by the sponsor and/or the project team during the regularly planned study deviation review meetings and the significant protocol deviations rules document can be updated.

All protocol deviations will be reviewed and assessed as to significance prior to the database lock. The list of protocol deviations (major or minor) that are additionally considered major clinically relevant for the purposes of analysis will also be identified and documented prior to the database lock.

All major protocol deviations will be summarized for all enrolled subjects. Major protocol deviations will also be presented in a listing.

5. Demographics and Baseline Characteristics

5.1 Demographics

Demographics such as age, sex, race, ethnicity, weight, height, BMI, and country will be summarized descriptively for the ITT Population. The age collected in CRF will be used for

analysis if it is non-missing. If the age is not collected in the CRF, the age in years is calculated using the date of the informed consent and date of birth.

Age (years) = [(Informed Consent Date – Date of Birth + 1) / 365.25].

BMI is calculated as:

 $BMI = (body weight in kilograms) / (height in meters)^2$.

Demographics for all subjects in the ITT set will be presented in a listing.

5.2 Medical History

Medical history will be coded using Medical Dictionary for Regulatory Activities (MedDRA) version 26.0 and listed by System Organ Class (SOC), Preferred Term (PT), and verbatim term. Medical history will also be summarized by disease group using frequencies and percentages with SOCs sorted in alphabetical order and PTs within each SOC in descending order of frequency for all subjects in the ITT population.

A by-subject listing of medical history will be provided.

5.3 Inclusion and Exclusion Criteria

Prior to enrollment, the investigator will assess if the subject fulfills all of the inclusion and none of the exclusion criteria outlined in the protocol (sections 11.1 and 11.2). The specific inclusion criterion not met or exclusion criterion which was met will be recorded in the eCRF. This information and whether the sponsor granted a waiver will be presented in a listing.

5.4 Fungal Disease

The fungal disease and site of infection, as confirmed by the DRC, will be presented in a listing.

5.5 Enrollment Categories

The enrollment categories, as confirmed by the DRC, will be presented in a listing.

5.6 Evidence of Ongoing Infection at Baseline

The evidence of ongoing infection at Baseline, as confirmed by the DRC, will be summarized in a table and presented in a listing.

6. Treatment and Medications

6.1 Prior and Concomitant Medications

All medications (including prescription and over-the-counter medications, supplements, and herbal products) taken from 28 days before Baseline/Day 1 through EoT will be recorded on the eCRF. Only the use of antifungal medications, antibiotics for any reason or medications to treat an AE will be recorded after EoT and through the Week 6 Follow-up visit. Start and stop times of concomitant medications taken during antifungal therapy will be recorded on the eCRF. Subjects will also record any new concomitant medications taken between visits in the subject diary.

All prior and concomitant medications will be coded using the web-based version of the World Health Organization Collaborating Centre (WHOCC) ATC/DDD Index 2023 and summarized based on the ITT population. A by-subject listing of prior and concomitant medications will be provided.

6.1.1 Prior Medications

Prior medications are defined as medications taken and stopped prior to the first dose of study drug. The number and percentage of subjects who took prior medications will be presented by WHO therapeutic drug class and generic drug name.

6.1.2 Concomitant Medications

Concomitant medications are defined as medications that are ongoing at or started after the first dose of study drug and started on or before the FU visit date, regardless of whether the stop date is missing. Medications with a stop date after the first dose of study drug are also considered concomitant medications. Medications with incomplete or missing dates will be handled as detailed in Section 3.3. A summary showing the number and percentage of subjects who took concomitant medications will be presented by WHO therapeutic drug class and generic drug name.

6.2 Study Treatments

Please refer to Section 2.3 for the details of the study treatment. Data related to the study treatment will be presented in a listing.

6.2.1 Study Participation Calculation and Extent of Exposure

The duration of study participation (days) is calculated as date of Study Completion/Termination recorded on the End of Study page – first dose date + 1. If the date of Study

Completion/Termination on the End of Study page is missing, or if a subject is lost to follow-up, the latest available visit date will be used.

The duration of study treatment (days) is calculated as last dose date – first dose date + 1.

The cumulative doses taken across the treatment period will use the exposure and missed dose log. All enrolled subjects will receive an initial oral loading dose of 750 mg of ibrexafungerp (3 tablets of 250 mg) BID during the first 2 days of treatment and then subsequent oral doses of 750 mg QD for up to 90 days. The missed dose log will be used to subtract the total number of missed doses from these total cumulative doses.

The duration of study participation, duration of study treatment, and the cumulative doses will be summarized by summary statistics. All this exposure information will be presented in a listing.

6.2.2 Treatment Compliance

Treatment compliance is defined as the ratio of total study dose to the planned dose, in terms of percentage. Treatment compliance will be summarized descriptively.

Treatment compliance = the cumulative dose / the planned dose *100%. The planned dose is defined as 2 doses for the first 2 days and then 1 dose for up to 90 days.

The treatment compliance will be classified as 0, 25%, 50%, 75%, and $\geq 100\%$. This categorical data will be summarized with the frequency and percentage of subjects.

7. EFFICACY

The primary efficacy and secondary efficacy endpoints will be performed on the ITT and PP populations. The ITT analyses will be considered primary and the PP analysis will be considered supportive of the primary analyses on the ITT population.

The primary efficacy endpoint of the study is the percentage of subjects who achieve Global Success at EOT, as determined by the DRC. Secondary efficacy endpoints include the percentage of subjects with a recurrence of the baseline fungal infection 42 days after EoT (Week 6 Follow up) as determined by the DRC, and the percentage of subjects surviving 42 and 84 days after Day 1 (first dose of study drug).

Efficacy outcomes will be based on definitions captured in Table 3. Criteria for the Investigator is outlined in Section 7.3.

Additional efficacy endpoints to be evaluated are in Section 7.3.

7.1 Primary Endpoint

The primary efficacy objective is to evaluate the efficacy of ibrexafungerp as determined by a DRC by assessing global success (composite assessment of clinical and mycological success) at EoT. The primary efficacy endpoint of the study is the percentage of subjects with global success (complete or partial global response) at EoT as determined by the DRC. Global outcome will be scored as global success (complete global response or partial global response) or global failure (stable disease or progressive disease) or Unable to determine – due to missing data.

Global Response	Outcome Criteria
Success	Complete Global Response: Complete clinical response (the
	resolution of all clinical signs and symptoms and/or radiological
	abnormalities from baseline attributable to the Candida auris
	infection) and a mycological response (mycological clearance
	(direct and/or negative cultures [when obtainable] and/or normal
	serological results [when appropriate])
	Partial Global Response: Partial clinical response (major
	improvement of all clinical signs and symptoms and/or
	radiological abnormalities from baseline attributable to the
	Candida auris infection) and a mycological response
	(mycological clearance (direct and/or negative cultures [when
	obtainable] and/or normal serological results [when appropriate])
Failure	Stable Disease: Minor or no clinical improvement but without
	deterioration and/or unchanged serological response.
	Progressive Disease: Clinical deterioration necessitating
	alternative antifungal therapy or resulting in death, and/or
	worsened serological response, and/or persistence of fungal
	infection on the basis of culture, microscopic evaluation, or
	histopathological testing.
^a Not Evaluable	Outcome cannot be assessed due to missing data

^aCategory added for non-evaluable subjects due to missing data

7.1.1 Primary Analysis

The primary efficacy analysis will be performed at EoT. A responder analysis will be performed on the number and percentage of subjects with Successful Global Response as determined by the DRC will be presented with a 95% confidence interval (CI) for a single binomial proportion in the ITT and PP populations. The Clopper Pearson method will be used for the confidence interval. If Global Response has not been deemed a success or failure, the outcome will be categorized as not evaluable. A responder is defined as a subject with either a success or a failure. A response of not evaluable will not be included in the analysis.

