7.3 Exploratory Endpoints

Exploratory categorical endpoints will be presented with 95% CIs for the ITT and PP populations using the same approach as for the primary endpoint.

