7.3.1 Exploratory Analyses

A responder analysis will be performed on the following endpoints. If the outcome cannot be assessed due to missing data, it will be categorized as not evaluable. A responder is defined as a subject with a response other than not evaluable. A response of not evaluable will not be included in the analysis.

- Percentage of subjects for each global response (complete response, partial response, stable disease, progressive disease) EoT, as determined by the DRC
- Percentage of subjects with clinical success at EoT, as determined by the investigator and DRC
- Percentage of subjects for each clinical response (complete response, partial response, stable response, progression of fungal disease, death) at EoT, as determined by the DRC

- Percentage of subjects with mycological success at EoT, as determined by the investigator and DRC
- Percentage of subjects with global success at EoT, as determined by the investigator

Additional exploratory analyses:

- All cause mortality at Day 30
- Analysis of response by minimum inhibitory concentration (MIC) based on CLSI M27-A3 *in vitro* method and EUCAST method at Screening

The following exploratory analyses were not originally included in the protocol:

- Evidence of ongoing infection at Baseline as determined by the DRC
- Causal relationship of death in the opinion of the DRC (if death is reported at any time during the study)
- Global response by site of infection (candidemia only, Pleural/Pulmonary, Intraabdominal/Pelvic, Soft tissue/wound, Bone and joint, Urinary tract, other)
- Global response by reason for enrollment (primary, refractory, intolerance to SOC, stepdown)
- Global response by region (India, Pakistan, South Africa)
- Global response by Age (,65; >= 65 years)
- Global response by neutropenia (ANC < 500) vs non neutropenic

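### SAP 7.1.1 and 7.3.1 define a responder to include failures, which contradicts the endpoint; on the likelier reading the rule drops not-evaluable subjects from the ITT rate, against Protocol 20.4

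*SAP*

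**What the plan says.** SAP 7.1 sets the endpoint: "The primary efficacy endpoint of the study is the percentage of subjects with global success (complete or partial global response) at EoT", as judged by the Data Review Committee (DRC). Stable and progressive disease are failures. A third category, for outcomes that missing data make impossible to assess, was added to the response table.

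SAP 7.1.1 then gives four statements about the analysis:

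- The quantity: "A responder analysis will be performed on the number and percentage of subjects with Successful Global Response as determined by the DRC", with a 95% interval for one binomial proportion. "The Clopper Pearson method will be used for the confidence interval".
- The third category: "If Global Response has not been deemed a success or failure, the outcome will be categorized as not evaluable".
- The definition: "A responder is defined as a subject with either a success or a failure".
- The exclusion: "A response of not evaluable will not be included in the analysis".

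SAP 7.3.1 has a parallel definition for the exploratory endpoints: "A responder is defined as a subject with a response other than not evaluable". SAP 7.3 says these endpoints are presented "using the same approach as for the primary endpoint", and SAP 7.2 says the same of recurrence. SAP 3.3 labels missing efficacy outcomes as unknown.

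SAP 7 makes the ITT analysis primary, and SAP 3.2 defines ITT as everyone enrolled. Protocol 20.4 assigns subjects without an EoT assessment as treatment failures in the efficacy analyses.

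**The concern.** A responder is ordinarily a subject who achieves the favourable outcome. Under SAP 7.1.1 a subject with stable or progressive disease is one too, and under SAP 7.3.1 so is a subject whose clinical response category is death. The only sentence that defines the term for the primary analysis therefore disagrees with SAP 7, SAP 7.1, Protocol 11.1 and Protocol 20.7.2, all of which count global success alone.

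SAP 1 says that table shells and data set specifications will be built from this document, so the wording can pass directly into a derived variable. The trial has one arm, and its main efficacy result is a single proportion. Protocol 12.1 intends to set the results against historical standard-of-care patients. The numerator and denominator of that proportion therefore need to be unambiguous.

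**Working it through.** The documents state no expected response rate, power or sample-size figure for this endpoint, so there is no planned figure to reproduce. The check is algebraic, followed by an illustration.

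**Inputs.** Planned N is about 30 (SAP 3.1). Let S be successes, F failures and U not-evaluable outcomes, with S + F + U = N in the ITT population. Intervals are exact 95% Clopper-Pearson, as in SAP 7.1.1. All S, F and U counts below are assumptions.

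**Three rates that the texts can produce**

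1. Definition used as the numerator, not-evaluable outcomes excluded: (S+F)/(S+F) = 100% always. With S = 0 and F = 30 it is 30/30 = 100% (88.4 to 100).
2. Responder read as evaluable subject, with global success as the numerator: S/(S+F). This can take any value from 0% to 100%. For example, 0/30 gives 0% (0 to 11.6) and 24/30 gives 80.0% (61.4 to 92.3).
3. Protocol 20.4, if every not-evaluable subject lacks an EoT assessment: S/(S+F+U).

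**Gap between rates 2 and 3**

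S/(S+F) − S/(S+F+U) = S·U / [(S+F)(S+F+U)]

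This is never negative. Whenever S and U are both above zero, exclusion raises the reported rate.

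**Illustration, N = 30**

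| S, F, U | Rate 1 | Rate 2 | Rate 3 | Gap (2 − 3) |
|---|---|---|---|---|
| 20, 7, 3 | 27/27 = 100% (87.2 to 100) | 20/27 = 74.1% (53.7 to 88.9) | 20/30 = 66.7% (47.2 to 82.7) | 20·3/(27·30) = 7.4 points |
| 18, 6, 6 | 24/24 = 100% (85.8 to 100) | 18/24 = 75.0% (53.3 to 90.2) | 18/30 = 60.0% (40.6 to 77.3) | 18·6/(24·30) = 15.0 points |

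**Which reading is likelier.** The definition sits between the sentence that creates the not-evaluable category and the sentence that excludes it. The parallel wording in SAP 7.3.1 covers endpoints with four or five categories, where a responder cannot be the numerator. Both point to rate 2.

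**Where it applies.** The PP population already requires an EoT assessment (SAP 3.2), so the conflict with Protocol 20.4 falls on the ITT analysis, which is the primary one.

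**The case against.** A reader might infer that the primary result of this trial is bound to be 100%, and so meaningless. The documents do not support that. SAP 7.1.1 itself names successful global response as the quantity presented, SAP 7 and 7.1 define the endpoint as global success, and nowhere is a percentage of responders promised. The SAP also uses response loosely for any outcome category: its global response table has rows for success, failure and not evaluable. A careful programmer would probably compute S/(S+F), and a flat 100% would be noticed. This part of the objection stands.

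It can also be said that the carry-over to other endpoints is limited. Recurrence has its own definition in SAP 7.2, several exploratory endpoints name their favourable outcome, and the reference to the primary approach most naturally means the interval method. That is largely right. What remains open for those endpoints is the denominator.

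Finally, the study is exploratory and descriptive, and the SAP openly notes that it added the not-evaluable category. But noting a new category is not the same as saying that it replaces the protocol's failure rule, and the SAP does not say so. Reading the word as evaluable subject removes the absurdity, but it leaves the wrong term and the conflict over the denominator.

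**Conclusion.** The definition is wrong as written and should be corrected before the shells are programmed. Taken literally as the numerator it gives 100% whatever the data, though that is not the likelier reading. On the likelier reading the primary ITT rate omits not-evaluable subjects, contrary to Protocol 20.4 for those without an EoT assessment, and the omission can only leave the rate unchanged or raise it. In the two assumed examples it rises by 7.4 and 15.0 percentage points.

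The size rests on two assumptions: the counts, which the documents do not give, and that every not-evaluable subject lacks an EoT assessment. Protocol 20.4 does not expressly cover a subject who was assessed at EoT but whose outcome could not be scored. To the extent that such subjects make up U, the gap attributable to the protocol conflict is smaller.

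**What to change.** In SAP 7.1.1 replace the definition with: *A responder is a subject with DRC-determined complete or partial global response at EoT; every other subject in the population, including subjects without an EoT assessment, is a non-responder.* This also settles subjects who were assessed but could not be scored, by counting them as non-responders. The SAP should state that choice openly.

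In the same edit:

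- Delete or amend the sentence of SAP 7.1.1 that excludes not-evaluable outcomes, and align the unknown category in SAP 3.3. Otherwise the new definition and the old exclusion would contradict each other.
- If wanted, keep the success rate among evaluable subjects as a labelled sensitivity analysis, with the number not evaluable shown beside it.
- In SAP 7.3.1 remove the general responder sentence, and name the positive outcome and the denominator for each endpoint.

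The cost is a few sentences of SAP text, one derived variable and possibly a lower reported rate. Replacing responder by evaluable subject would cure the label alone and leave the conflict with Protocol 20.4 in place.
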